### 2.3 Exploratory Outcomes

#### Clinical Exploratory Outcomes

- Symptoms measured by CAT score and EQ-5D-5L from baseline to week 8.

**Biological Exploratory Outcomes\***

- Neutrophil activation biomarkers that may include but are not limited to measurement of neutrophil elastase and ICAM-1.
- Inflammatory response biomarkers that may include but are not limited to measurement of proteins, metabolites, cytokines (including but not limited to TNF $\alpha$ , IL-1 $\beta$ , IL-6, IL-8), proteases and anti-proteases.
- Nucleic acid analysis in sputum and blood including, viral/bacterial nucleic acid detection and gene expression. RNA sequencing, mRNA analysis and methylation analysis.

**Exploratory Bronchoscopy Sub-study Outcome Measures\***

- Measurement of epithelial ICAM-1 and airway neutrophilic inflammatory markers.
- Bronchial biopsy histology and immunohistopathology.
- Indices of nucleic acid expression in sputum and blood including viral and genomic DNA, viral RNA, microRNA and mRNA analysis & methylation analysis.

\*These analyses are being undertaken outside of the NICTU and are not detailed in this statistical analysis plan

## **3. DATA**

### **3.1 CRF Forms and variables**

Full details of data collection and timing are described in the trial protocol (Version 4.0 / 22/04/2020). A copy of the CRF is presented in the Trial Master File (TMF).

### **3.2 Management of datasets**

Below is the standard policy for management of data in the CTU as given in the CTU SOPs, at the time of analysis (including DMEC reports/Interim analysis (if required)):

Page **11** of **44**

The trial database will be stored in MACRO:

DMEC reports: - In collaboration with the Statistician, the Data Manager will create MACRO output files to support the analysis. This will act as the frozen dataset. It is the responsibility of the statistician to accurately record the date of freezing and ensure all data is retrieved. If there are no errors, the study database will be re-opened for further data entry.

If there are errors, the Study Statistician will report these to the Data Manager. The Data Manager in consultation with the Study Statistician, Data Project Manager and Senior Statistician will resolve the errors and determine which of the database closure activities are required to be undertaken. The Data Manager will re-create the MACRO output files to support the analysis. Database closure & lock: The same process for DMEC reporting will be followed for database closure and lock, the only difference being when the MACRO output files are created and there are no errors found for final analysis, the database should be locked as per SOP DM09.

### 3.3 Data completion schedule

The following table describes the schedule of assessments:

**Table 1: Schedule of Assessments EViSCO Study**

	Screening	Visit 1	Visit 2 week 4 (+/- 7days)	Visit 3 week 8 (+/- 7days)	Follow up week 12
Informed Consent	X				
Inclusion/Exclusion Criteria	X				
Demographic Data	X				
Medical History	X	X			
Medications	X	X	X	X	
Vital signs & BMI		X			
Documentation of exacerbations	X	X	X	X	X
Randomisation/Registration		X			
CAT		X	X	X	
EQ-5D-5L		X	X	X	

Lung Function*	X			X	
Blood sample**	X	X		X	
Drug administration		X	X		
Sputum sample	X	X	X	X	
Bronchoscopy***		X		X	
Adverse events		X	X	X	X

\*In some cases it may not be possible to facilitate lung function testing at the screening visit. In such cases patients who otherwise meet the trial eligibility criteria will be invited to return to have lung function measurement in order to complete the screening procedures. Confirmation of lung function indices must occur prior to trial enrolment.

\*\*At the screening visit a U&E sample will only be sent if there are no previous U&E results from the previous 4 months. A screening U&E sample may be repeated at the discretion of the researcher if there is clinical concern that historic values are borderline.

\*\*\*Bronchoscopy will only be performed in participants that consent to the sub-study. In addition bronchoscopy may not be undertaken on the same day as visit 1 and visit 3 but ideally will be facilitated within the bronchoscopy list.

### 3.4 Data verification

Data verification, consistency and range checks will have been performed at the data entry stage by the CTU, as well as checks for missing data (copies can be found in the TMF) according to SOP DM04. Additional range, consistency and missing data checks will be performed, as appropriate, when the analysis is performed (and when the datasets for analysis are constructed). All variables will be examined for unusual, outlying, unlabelled or inconsistent values.

Given the thorough nature of our follow-up procedure we expect the issue of missing data to be relatively minimal. We anticipate high compliance with initial data collection as this is close to the time of patient registration. If any clinical data is missing imputation will not be done. We expect there to be minimal data missing regarding study drug compliance, if a subject has compliance recorded for only one visit we will assume their overall compliance rate based on any compliance data captured.

Any problems with trial data will be queried with the Trial Managers, Data Managers, or statisticians, as appropriate. If possible, data queries will be resolved, although it is accepted that due to administrative reasons and data availability a small number of problems will continue to exist. This will be minimised.

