## 9.3 Study Drug Supply

Study drug packs will be packaged and labelled by Victoria Pharmaceuticals, [name]. Study drug packs consist of:

Valaciclovir 500mg capsules in bottles containing 210 capsules

Matched placebo (Avicel®PH) capsules in bottles containing 210 capsules

Study drug packs of valaciclovir 500mg or placebo capsules will be labelled in compliance with the applicable regulatory requirements. Study drug packs will be dispatched to the responsible site pharmacist under the instruction of the CI or designee. The CI or designee will monitor the quantity of study drug packs at site to ensure study drug packs are available to facilitate the supply of study drug to patients at the time of recruitment/randomisation and at subsequent study visits.

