## 9.7 Study Drug Administration

Patients will take valaciclovir 1 gram (2 x 500mg capsules) or matching placebo capsules orally three times daily for 8 weeks .

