### 2.2 Secondary outcome measures

- Lung function measured by spirometry, the principal component will be the change in FEV1 from baseline to week 8\*.
- Participant compliance measured by total number of tablets administered as a proportion of total number of tablets supplied.

\* In light of the COVID19 lockdown lung function will not be measured in order to prevent unnecessary risk of exposure to study participants.

\*\* Blood samples will no longer be taken in order to prevent unnecessary risk of exposure to study participants.

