## 4. DEFINITION OF TERMS

Term	Definition
Adverse Event (AE)	Any untoward medical occurrence in a participant to whom a medicinal product has been administered including occurrences which are not necessarily caused by or related to that product.
Adverse Reaction (AR)	Any untoward and unintended response in a participant to an investigational medicinal product, which is related to any dose administered to that participant.
Unexpected Adverse Reaction (UAR)	An adverse reaction the nature and severity of which is not consistent with the Reference Safety Information.
Serious Adverse Event (SAE) Serious Adverse Reaction (SAR)	An adverse event or adverse reaction that:  results in death, is life-threatening, requires hospitalisation or prolongation of existing hospitalisation, results in persistent or significant disability or incapacity, consists of a congenital anomaly or birth defect, or any other important medical event(s) that carries a real, not hypothetical, risk of one of the outcomes above.
Suspected Serious Adverse Reaction (SSAR)	Any adverse reaction that is classed in nature as serious and is consistent with the Reference Safety Information (RSI)
Suspected Unexpected Serious Adverse Reaction (SUSAR)	Any adverse reaction that is classed in nature as serious and is not consistent with the Reference Safety Information
The EBV suppression	The EBV suppression is defined as 90% reduction in the viral load.
Per Protocol	The pre protocol population is defined as patients with overall study drug adherence of at least 70%
Overall Study Drug Adherence	Total number of tablets administered i.e. actual number of capsules taken / expected number of capsules taken
MMEF	Mid Expiratory Flow – MMEF 25-75% (L/s).

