## 5. SAMPLE SIZE CALCULATIONS

A sample size of 31 subjects per group will have 90% power at a two-tailed significance level of 0.05 to detect a difference in the exploratory efficacy outcome EBV shedding of 70% in the treated group to 30% in the control group. With a dropout rate of approximately 30%, this study will require a total of 44 patients per group.

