## **Efficacy**

The number of patients experiencing suppression of Epstein-Barr virus in the two groups will be compared using Chi-Square test (or Fisher's exact if appropriate) followed by logistic regression adjusting for baseline FEV1 and other covariates if required. The odds ratio and 95% confidence interval will be reported.

The intention-to-treat basis analysis will use a significance level of  $\leq 0.05$  for the primary outcome. Per-protocol analysis will also be conducted which will involve a comparison of treatment groups that includes patients with overall study drug adherence of at least 70%. Subgroup analyses will be performed on the primary outcome for compliance. In order to assess differences in treatment effects between the subgroups we will report odds ratio and 99% CI from the treatment\*subgroup interaction model. Sensitivity analysis will be performed for the primary efficacy outcome excluding patients with a confirmed diagnosis of COVID-19

Additionally, change in viral load (Quantitative PCR) from baseline to week 8 in the two groups will be compared using independent t-test (or non-parametric alternative). The mean difference and 95% confidence interval will be reported.

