### **7.2 Analysis of secondary, exploratory and other safety outcomes**

The lung function outcomes will be reported using Mean (SD) or Median (p25 to p75) in patients with COPD. The change in lung function from baseline to week 8 in the two groups will be analysed using independent t-test or non-parametric alternative. The mean at baseline versus the mean at week 8 within each group will be analysed using a paired t-test or non-parametric alternative.

Exploratory subgroup analyses will be performed on the lung function outcomes for EBV suppression. Analysis of Covariance will be used to assess differences in

treatment effects between the subgroups and will be reported using mean difference and 99% CI.

Tolerability of valaciclovir will be assessed by measuring participant compliance at visit 2 and 3. The compliance (%) will be reported using mean (SD) or Median (p25 to p75) and will be analysed using independent t-test or non-parametric alternative

The change over time in CAT score and EQ-5D will be reported using Mean (SD) or Median (p25 to p75). The change from baseline to 8 weeks will analysed using independent t-test or non-parametric alternative.

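### The one-visit compliance rule makes no exception for patients who stopped drug, so a week 4 stopper with no visit 3 count can be scored 100% instead of 50%

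*SAP*

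**What the plan says.** The rule is in SAP 3.4: "if a subject has compliance recorded for only one visit we will assume their overall compliance rate based on any compliance data captured". It does not distinguish a missing count in a patient still on drug from a missing count in a patient who had stopped.

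Three parts of the plan use the result:

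- **Tolerability (SAP 7.2).** "Tolerability of valaciclovir will be assessed by measuring participant compliance at visit 2 and 3".
- **Per-protocol efficacy (SAP 7.1).** The comparison "includes patients with overall study drug adherence of at least 70" per cent.
- **Compliance subgroups (SAP 8.4).** The bands are 80% or more, 60 to 79%, and under 60%.

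The SAP gives two definitions of the quantity. SAP 4 defines overall adherence as "actual number of capsules taken / expected number of capsules taken", without saying what is expected of a patient who stops early. SAP 2.2 and 8.4 define the secondary outcome as "total number of tablets administered as a proportion of total number of tablets supplied".

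**The concern.** Compliance is counted only at visits 2 and 3. A patient who stops at visit 2 and takes no second bottle has nothing to count at visit 3. The telephone contact four weeks after stopping (Protocol 10.1.5) covers adverse events and exacerbations, not capsules. For such a patient the second count is missing because treatment ended, and intake in that period is in fact zero. The rule fills the gap with the rate from the period in which the patient was still taking the drug.

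Three results are at stake: a secondary outcome that is also the named tolerability measure, membership of the per-protocol set, and the compliance subgroup. In the last two, a patient who took half the course can be grouped with those who took all of it.

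**Working it through.** **Inputs**

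- Dose count, Protocol 9.7: "Patients will take valaciclovir 1 gram (2 x 500mg capsules) or matching placebo capsules orally three times daily for 8 weeks". That is 2 × 3 = 6 capsules a day, so 6 × 28 = 168 expected in four weeks and 6 × 56 = 336 in eight.
- Pack size, Protocol 9.3: "Valaciclovir 500mg capsules in bottles containing 210 capsules". One bottle is given at each of visits 1 and 2, so 2 × 210 = 420 if both are dispensed.
- Visit 2 window: week 4 ± 7 days, that is day 21 to day 35.
- Dropout, SAP 5: "With a dropout rate of approximately 30%, this study will require a total of 44 patients per group".

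**The plan's own figure.** For 70% v 30%, two-sided 0.05 and 90% power, with pooled variance and no continuity correction:

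n = (1.960 × √(2 × 0.5 × 0.5) + 1.282 × √(0.7 × 0.3 + 0.3 × 0.7))² / 0.4² = 30.7, rounded up to 31.

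Then 31/0.7 = 44.3, which the plan rounds to 44. The figure is reproduced. It is used here only to set a range: 30% of 44 is about 13.

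**One patient, taken/expected scale.** All capsules are taken until the stop, there is no visit 3 count, and the rule is read as carrying the recorded rate to the whole course.

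| Stop day | Taken | Score under the rule | Taken/336 |
|---|---|---|---|
| 21 | 126 | 100% | 37.5% |
| 28 | 168 | 100% | 50.0% |
| 35 | 210 | 100% | 62.5% |

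Every true value is below the 70% per-protocol cut and below the 80% band, yet the rule puts the patient in both. The day 28 stopper moves from the under-60% band to the top band. The day 35 stopper belongs in the 60 to 79% band.

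Intake to week 4 need not be perfect. With 70%, 80%, 90% or 100% to week 4 and nothing after, true adherence is half of that: 35%, 40%, 45% or 50%. All four pass the 70% cut under the rule. A patient with 100% to week 4 would need at least 40% of the second half to reach a true 70%, since (100 + 40)/2 = 70.

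**Arm mean, taken/expected scale.** Assume k of 44 stop at week 4 with no visit 3 count, and everyone takes all capsules while on drug. True mean = (100 × (44 − k) + 50 × k)/44.

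| k | True mean | Mean under the rule |
|---|---|---|
| 0 | 100% | 100% |
| 4 | 95.5% | 100% |
| 9 | 89.8% | 100% |
| 13 | 85.2% | 100% |

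**The taken/supplied scale.** A week 4 stopper never given a second bottle scores 168/210 = 80%. A patient who completes the full course scores 336/420 = 80%. This definition cannot tell them apart, with or without the one-visit rule. If the second bottle was dispensed and its count is missing, the rule gives 80% where 168/420 = 40%.

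**Per-protocol efficacy, outer bound.** Read 70% and 30% as suppression rates. Suppose 13 valaciclovir stoppers all give week 8 sputum and suppress at between 30% and 70%. The valaciclovir rate is then (31 × 70 + 13 × 30)/44 = 58.2% up to 70%. The difference from placebo is 28 to 40 points, and the odds ratio is 3.25 to 5.44.

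**The case against.** **The wording admits another reading.** Captured capsules over the full eight-week expectation would give 168/336 = 50%, the correct value. This is possible, but the SAP does not say so. An overall rate assumed from one visit's data more naturally means that the visit's rate stands for the whole. A sentence that can yield 100% or 50% for the same patient needs settling before analysis.

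**The reach is limited.** The rule acts only when exactly one count is missing. Patients who stop drug stay in follow-up (Protocol 7.3), and visit 3 is a telephone visit with a self-reported count (Protocol 10.1.4). A stopper with a recorded visit 3 count, including a recorded zero, is scored correctly. A patient who leaves before visit 2 has no count for the rule to use. SAP 3.4 expects little missing compliance data. All of this stands.

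**A reader might infer that the trial hides intolerance.** The documents do not support that. SAP 8.3 reports duration of study drug, reasons for termination and premature withdrawals by arm, and SAP 8.5 reports adverse events and reactions with risk ratios. Only the compliance measure is affected.

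**A reader might also take the 30% dropout as the number misclassified, or infer a hidden difference between arms of a given size.** Neither follows. Nothing says that dropouts leave at week 4 with one count, and no split by arm is given. The allowance raises 31 to 44, so it appears to cover patients without a primary outcome. Such patients cannot also enter the per-protocol efficacy comparison, which is why the per-protocol figures above are an outer bound and not an expectation.

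**Conclusion.** The concern holds in a limited form. On its natural reading, the SAP 3.4 rule gives a wrong value for one identifiable kind of patient: one who stopped drug around visit 2 and has no visit 3 count. On the taken/expected scale the score is 100% against a true 37.5% to 62.5%, enough to cross both the 70% cut and the 80% band. Per-protocol efficacy is affected only where such a patient supplies a week 8 sputum sample. The intention-to-treat primary analysis is not affected.

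The overstatement of an arm's mean compliance is 0 to 14.8 points (100 − 85.2) for 0 to 13 such patients of 44. Those counts, and full intake while on drug, are assumptions; the documents give no number. The direction for each affected patient is certain on this reading: the score is too high. The plan should be corrected, but the point does not threaten its main conclusion.

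The secondary outcome has a separate weakness. Its supplied denominator scores a week 4 stopper without a second bottle the same as a completer, so changing the one-visit sentence alone would not repair it.

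**What to change.** Amend SAP 3.4 and SAP 4 before unblinding:

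1. Use the planned eight-week expected count, 336 capsules, as the denominator for every patient.
2. Count capsules after a documented stop or withdrawal as not taken.
3. Extrapolate from one visit only for patients documented as still on drug whose other count is missing. Add a sensitivity analysis that sets the missing period to zero.
4. Apply the same taken/expected definition to the secondary compliance outcome (SAP 2.2 and 8.4; Protocol 5.3.2) in place of taken/supplied.

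The cost is a few sentences and no new data collection, with these consequences:

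- Reported mean compliance will be lower, and the per-protocol set smaller, wherever such patients exist.
- The stop date must be confirmed as available. Protocol 9.8 names only the reason for termination as recorded on the CRF; the duration of study drug in SAP 8.3 implies a date.
- Treatment continues until visit 3 at week 8 ± 7 days (Protocol 9.1). With a fixed denominator, a fully adherent patient can therefore score from 49 × 6/336 = 87.5% to 63 × 6/336 = 112.5%. Neither value crosses the 70% or 80% cut, but the SAP should say how values above 100% are shown.

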### 3.5 Data coding

The variable codings will be as specified on the CRF.

## 4. DEFINITION OF TERMS

Term	Definition
Adverse Event (AE)	Any untoward medical occurrence in a participant to whom a medicinal product has been administered including occurrences which are not necessarily caused by or related to that product.
Adverse Reaction (AR)	Any untoward and unintended response in a participant to an investigational medicinal product, which is related to any dose administered to that participant.
Unexpected Adverse Reaction (UAR)	An adverse reaction the nature and severity of which is not consistent with the Reference Safety Information.
Serious Adverse Event (SAE) Serious Adverse Reaction (SAR)	An adverse event or adverse reaction that:  results in death, is life-threatening, requires hospitalisation or prolongation of existing hospitalisation, results in persistent or significant disability or incapacity, consists of a congenital anomaly or birth defect, or any other important medical event(s) that carries a real, not hypothetical, risk of one of the outcomes above.
Suspected Serious Adverse Reaction (SSAR)	Any adverse reaction that is classed in nature as serious and is consistent with the Reference Safety Information (RSI)
Suspected Unexpected Serious Adverse Reaction (SUSAR)	Any adverse reaction that is classed in nature as serious and is not consistent with the Reference Safety Information
The EBV suppression	The EBV suppression is defined as 90% reduction in the viral load.
Per Protocol	The pre protocol population is defined as patients with overall study drug adherence of at least 70%
Overall Study Drug Adherence	Total number of tablets administered i.e. actual number of capsules taken / expected number of capsules taken
MMEF	Mid Expiratory Flow – MMEF 25-75% (L/s).

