### 8.3 Trial treatment

- Number of patients receiving at least one unit/dose of the drug, n(%) by treatment arm
- Duration of study drug (days), mean(SD) by treatment arm
- Overall compliance, mean(SD) by treatment arm
- Compliance, n(%) by treatment arm
- Time lapse between randomisation and study drug administration, mean(SD) by treatment arm
- Reason for study drug termination, n(%) by treatment arm
- Protocol Deviations/Violations, n(%) by treatment arm
- Premature withdrawals, n(%) by treatment arm

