	No	n (%)	n (%)	n (%)
Quantitative PCR Titre(copies)		xx.x (xx.x)	xx.x (xx.x)	xx.x (xx.x)

Relevant co-morbidities		n (%)	n (%)	n (%)
Pre-existing Cardiovascular issues		n (%)	n (%)	n (%)
Any exacerbations in past 12 months	Yes	n (%)	n (%)	n (%)
	No	n (%)	n (%)	n (%)
If Yes, Number of exacerbations in past 12 months		x.x (x.x to x.x)	x.x (x.x to x.x)	x.x (x.x to x.x)
If Yes, Number of exacerbations in past 12 months requiring steroids		x.x (x.x to x.x)	x.x (x.x to x.x)	x.x (x.x to x.x)
If Yes, Number of exacerbations in past 12 months requiring antibiotics		x.x (x.x to x.x)	x.x (x.x to x.x)	x.x (x.x to x.x)
If Yes, Number of exacerbations in past 12 months resulting in hospitalization		x.x (x.x to x.x)	x.x (x.x to x.x)	x.x (x.x to x.x)

Mean (SD) (or median (IQR)) presented for continuous variables and no. (%) for all categorical variables.

Table x.x: Treatment after Trial Entry Treatment Termination, Protocol Deviation

		Valaciclovir N = <n>	Placebo N = <n>
Number of patients who received at least one dose of treatment		n (xx.x%)	n (xx.x%)
Duration of study drug (days)		xx.x (x.x)	xx.x (x.x)
Overall compliance		xx.x (x.x)	xx.x (x.x)
Compliance	≥80%	n (xx.x%)	n (xx.x%)
	60-79%	n (xx.x%)	n (xx.x%)
	<60%	n (xx.x%)	n (xx.x%)
Time from randomisation to start of study drug (hours)		xx.x (xx.x to xx.x)	xx.x (xx.x to xx.x)
Reasons for termination of study drug			
1) Study Drug related AE		n (xx.x%)	n (xx.x%)
2) Study Drug related SAE		n (xx.x%)	n (xx.x%)
3) Study Drug Expiry Date		n (xx.x%)	n (xx.x%)
4) Patient Request		n (xx.x%)	n (xx.x%)
5) Clinician's Request		n (xx.x%)	n (xx.x%)
6) Other		n (xx.x%)	n (xx.x%)
Protocol deviations/ violations			
Eligibility		n (xx.x%)	n (xx.x%)
Consent		n (xx.x%)	n (xx.x%)
Study Drug Administration			
Did not receive allocated treatment a		n (xx.x%)	n (xx.x%)
Received treatment of other group b		n (xx.x%)	n (xx.x%)
Study drug omitted in error c		n (xx.x%)	n (xx.x%)
Study drug received in error		n (xx.x%)	n (xx.x%)
SAE reporting timelines		n (xx.x%)	n (xx.x%)
Visit outside schedule		n (xx.x%)	n (xx.x%)
Other		n (xx.x%)	n (xx.x%)
Premature Withdrawals			
Adverse Event		n (xx.x%)	n (xx.x%)
Serious Adverse Event		n (xx.x%)	n (xx.x%)
Protocol deviation/ non-compliance		n (xx.x%)	n (xx.x%)
Lost to Follow Up		n (xx.x%)	n (xx.x%)
Withdrawal of patient consent		n (xx.x%)	n (xx.x%)
Death		n (xx.x%)	n (xx.x%)

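### The per-protocol set is defined by capsule adherence alone, so it keeps patients with major deviations that the SAP itself records, and the supportive per-protocol estimate may be biased

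*SAP*

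**What the plan says.** SAP section 4 defines the set in one line: "The pre protocol population is defined as patients with overall study drug adherence of at least 70" per cent (the first word is evidently meant as 'per'). Adherence in the same table is "actual number of capsules taken / expected number of capsules taken", a ratio of capsule counts that does not mention which treatment the capsules contained.

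SAP section 7.1 (Efficacy) describes the analysis as a "comparison of treatment groups that includes patients with overall study drug adherence of at least 70" per cent, again with no other condition. Protocol section 13.2 names only intention-to-treat and gives no per-protocol rule.

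Deviations are handled separately. SAP section 8.3 lists "Protocol Deviations/Violations, n(%) by treatment arm". The treatment and deviation table in Appendix 1 has an Eligibility row and rows for "Received treatment of other group" and "Visit outside schedule". Nothing links these rows to the per-protocol set.

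In the Appendix 1 primary efficacy table, two of the four rows are per-protocol (suppression, and change in viral load), each with a p-value. The intention-to-treat suppression row is marked as primary.

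**The concern.** A per-protocol analysis is meant to show the effect in patients who were eligible, took the treatment they were allocated and were measured when planned. Capsule counts establish none of these. A patient allocated to placebo who took every capsule from a valaciclovir bottle is 100% adherent and so belongs to the set. So does an adherent patient who should not have been enrolled, or whose week-8 sputum came outside the window. The SAP can list a patient as a deviation in one table and count the same patient as per protocol in another.

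What is at stake is how the supportive analysis is read. If the per-protocol and intention-to-treat results agree, that is usually taken as evidence that deviations did not drive the result. Here both would contain the same eligibility, wrong-arm and timing deviations, so agreement would say little about them.

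**Working it through.** **Inputs.** Suppression 70% v 30%, 31 per group, two-sided 0.05 and 90% power come from Protocol section 13.1 and SAP section 5. The number of wrong-arm patients is not given; k = 1, 2 or 3 per arm out of 31 is an assumption.

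**The plan's own figure.** n = [1.960 × √(2 × 0.5 × 0.5) + 1.282 × √(0.7 × 0.3 + 0.3 × 0.7)]² / 0.4² = 30.7, so 31 per group, as stated. For dropout, 31 / 0.7 = 44.3 against the stated 44, which agrees to within rounding.

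**Membership.** Applying the SAP's rule literally to a patient with adherence of at least 70%:

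| Deviation recorded in Appendix 1 | Any rule removing the patient? |
|---|---|
| Eligibility breach | None |
| Other group's treatment | None |
| Visit outside schedule | None |

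**Wrong-arm patients, analysed as randomised.** With k swapped patients in each arm, the valaciclovir rate is 0.7 − 0.4k/31, the placebo rate is 0.3 + 0.4k/31, and the difference is 0.4 × (1 − 2k/31). Exact power sums the binomial probabilities of all tables in which the uncorrected chi-square test gives p ≤ 0.05. Exclusion leaves 31 − k per arm at 70% v 30%.

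| k per arm | Rates | Difference (points) | Odds ratio | Exact power, kept | Exact power, excluded |
|---|---|---|---|---|---|
| 0 | 70.0% v 30.0% | 40.0 | 5.44 | 91.1% | 91.1% |
| 1 | 68.7% v 31.3% | 37.4 | 4.82 | 86.9% | 89.6% |
| 2 | 67.4% v 32.6% | 34.8 | 4.28 | 81.5% | 87.9% |
| 3 | 66.1% v 33.9% | 32.3 | 3.81 | 75.1% | 86.1% |

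Exclusion returns the difference to 40 points and the odds ratio to 5.44. It does not return power to 91%, because the set is smaller.

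**Ineligible patients.** If the breached criterion has no bearing on viral response, the rates stay at 70% and 30% and nothing changes (40 points, odds ratio 5.44). If the patient had no measurable virus at baseline and is counted as not suppressed (an assumption), the rates become 0.7 × (1 − k/31) and 0.3 × (1 − k/31). For k = 1, 2 and 3 the difference is then 38.7, 37.4 and 36.1 points, and the odds ratio 5.13, 4.86 and 4.63.

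**Out-of-window samples.** The documents point in more than one direction:

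- Protocol section 3.2 says the virus is usually suppressed after two weeks, so an early sample need not miss the effect.
- Protocol section 9.1 keeps patients on treatment until visit 3. Sections 9.3, 9.6 and 9.7 give two bottles of 210 capsules at six a day, and 420 / 6 = 70 days, so a late sample may still be taken on drug.
- Protocol section 9.8 refers to a maximum of 8 weeks, so a late sample may also be taken off drug. Section 3.1 reports that shedding recurred in infectious mononucleosis once aciclovir was withdrawn.

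No figure in the documents allows a direction or size to be calculated.

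**The case against.** The strongest reply is that little depends on this. Intention-to-treat is the primary analysis. The only bias shown is towards no difference, in a supportive analysis of a superiority comparison, so it cannot manufacture an efficacy claim. Deviations will be reported by arm, and a reader can see whether any occurred. All of this stands and limits the severity.

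The wrong-arm illustration is also open to challenge. It needs 2 to 6 of 62 patients fully crossed over, evenly in both arms. Drug is dispensed at two visits, so full crossover requires two wrong packs. Under Protocol section 8.1 the pharmacist confirms the pack numbers for both visits, and under SAP section 6.1 the trials unit checks the identifier against the randomisation schedule. Nothing in the documents suggests errors at that rate; a row in a template table is not evidence of any. The SAP also does not say whether the per-protocol comparison is by allocated or received treatment, so the dilution rests on reading it as allocated. These objections stand as limits on size. They do not supply the missing exclusion rule.

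A reader might infer that all three kinds of deviation dilute the result. The documents support that only for wrong-arm patients analysed as randomised. A reader might also take the per-protocol comparison as the only planned efficacy estimate in patients who took their treatment. It is not: SAP sections 7.1 and 8.4 also plan an odds ratio by compliance, including a stratum of 80% or more. That stratum too rests on capsule counts, so it does not fill the gap.

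**Conclusion.** The point holds as a gap in the definition of a supportive analysis. Followed exactly, the plan keeps adherent patients with recorded major deviations in the per-protocol set, and the estimate may be biased. For wrong-arm patients the bias is towards no difference, provided they are analysed as randomised. For ineligible patients it depends on whether the breached criterion affects the viral endpoint. For samples outside the window it is unknown in both direction and size.

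The figures (a difference of 37.4 to 32.3 points instead of 40, and an odds ratio of 4.8 to 3.8 instead of 5.4) illustrate an assumed 1 to 3 symmetric swaps per arm at the plan's rates. They do not predict what happened. The 31 per arm is the plan's sample-size figure before inflation for dropout; no size or power is planned for the per-protocol set itself.

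It would be wrong to infer that the primary efficacy conclusion is compromised. That conclusion rests on intention-to-treat and is untouched. Severity is minor, and the correction is worth making because it is cheap and is credible only if made before the treatment code is used.

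**What to change.** In SAP sections 4 and 7.1, define the per-protocol set as patients who:

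1. meet the existing adherence rule;
2. received only their allocated treatment;
3. have no major eligibility deviation, in particular none bearing on the presence of EBV in sputum;
4. gave the week-8 sputum within the existing window of +/- 7 days.

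State which eligibility deviations count as major. Fix the whole rule, and settle the eligibility and timing exclusions patient by patient, while blind and before the treatment code is used. The wrong-arm exclusion cannot be settled in the same way, because footnote b to the Appendix 1 table says those counts come from the randomisation listing held by the trial statistician. Write that exclusion in advance and apply it mechanically once the listing is used. Leave the intention-to-treat primary analysis as it is.

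The cost is a change of SAP wording and a blind review of deviations that the SAP already plans to report. The downside is a slightly smaller per-protocol set: in the illustration above, 28 to 30 per arm instead of 31.
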